## 10.1 Screening and Enrollment

*Subjects may complete study procedures at both sites (e.g., baseline MRI at UW and Month 3 MRI at MCW) and any individual subject's data may be collected between sites depending on subjects' ability to travel between sites, study team availability, and investigator approval. Subjects may be dispersed interchangeably and unevenly between sites based on, for instance, subject convenience, study team availability, the site's ability to collect data, and/or the study team's preference to complete datasets. If a subject is unable to complete all study procedures prior to the end of study funding, they may choose to complete remaining study procedures at the main site if deemed eligible by the study investigator*

The Screening and Enrollment visits and procedures are described in detail below.

### Pre-screening

Participants will be screened by telephone for major inclusion and exclusion criteria. Eligibility may be determined by screening existing records. Some ineligibility criteria may become known during the course of the study, for example, development of new medical conditions or abnormality detected on brain imaging that may change the participant's eligibility.

### Decisional Capacity

It should be noted that all participants enrolled must retain decisional capacity at their baseline visit. The only situation where we indicate a plan to obtain assent from a participant is when a patient with MCI loses capacity over the course of the study and has indicated to their legally authorized representative that they wish to continue in the study even after losing decisional capacity. In this case, assent will always operate as a veto to the subject's participation, despite the surrogate's preference. Assent will always be verified prior to and during any study procedures.

### Baseline Visit

Prior to any procedures, informed consent will be obtained. Visit procedures may take up to 7 hours but may be more or less depending on time needed for breaks, participant comfort, and scanner set-up. This baseline visit will likely be completed over 2-3 days but can be completed over multiple days prior to Visit 2.

Once consent is obtained, the following assessments will be completed, and information collected for study participants.

- Document informed consent
- Review eligibility based on inclusion/exclusion criteria
- Demographics (age, sex, race, ethnicity, age, year of birth)
- Medical history
- Physical and Neuro exam including vitals
- Medications
- Cognitive battery
- Structural MRI
- TMS Neuro-navigation (MCW only)
- Study Partner Questionnaires

### Vitals and Medical Evaluation

Vitals include height and weight measurements, resting blood pressure, body temperature, heart rate, and respirations. Physical and neurological examinations will be conducted by clinicians and include a review of systems.

**Interviews and questionnaires:**

Participants will be interviewed by staff for completion of questionnaires intended to clarify medical history and level of awareness of cognitive deficits.

Study partners will complete three questionnaires designed to assess the subject's cognitive function and ability to perform activities of daily living. These questionnaires include:

- Alzheimer's Disease Cooperative Scale - Activities of Daily Living – Mild Cognitive Impairment (ADCS-ADL-MCI)
- Lawton-Brody Instrumental Activities of Daily Living Scale (Lawton IADL)
- Short Form of the Informant Questionnaire on Cognitive Decline in the Elderly (Short IQCODE)

**Cognitive Battery**

Participants will complete a broad battery of neuropsychological tests administered by trained personnel; this comprehensive battery will include the Alzheimer's Disease Cooperative Study-Preclinical Alzheimer Cognitive Composite (ADCS-PACC), which will serve as the primary outcome measure for the future phase II trial (see Table 5). The ADCS-PACC is a composite of 4 measures with well-established sensitivity for the detection of cognitive decline in prodromal and mild dementia. The final score is determined from its components using an established normalization method; the four Z scores are then added to form the composite. Consequently, a change of 0.5 standard deviations on each component would correspond to a 2-point change on the composite. We will alternate between 3 different versions of the test in order to minimize the risk of learning effects (Donohue et al., 2014).

The ADCS-PACC emerged as a response to concerns about ceiling effects, and the insensitivity to early stage deficits and to cognitive change of more standard Alzheimer's disease measures (e.g. ADAS-Cog). The PACC is currently being used as the primary outcome measure in multiple ongoing studies of early or preclinical Alzheimer's disease (Donohue et al., 2014; Harrison, 2018).

**Table 5. ADCS-PACC**

Cognitive Subdomain	Test
Episodic Memory	Rey Auditory Verbal Learning Test (RAVLT) (or Free and Cued Selective Reminding Test (FCSRT) (0-48 points)
	Logical Memory IIa sub-test from the Wechsler Memory test (0-25 points).
Orientation	Mini Mental Status Examination (MMSE) (0-30 points).
Executive function	Digit Symbol substitution test (DSST) from the Wechsler Adult Intelligence Scale-Revised (0-93 points).

The neuropsychological test battery will include a multidimensional set of brief measures assessing cognitive, emotional, motor and sensory function that can be used as a "common currency" across diverse study designs and settings which will be supplemented by measures that are consistent with other national studies of Alzheimer's disease (see Table 6).

**Table 6. Cognitive Battery (Secondary Outcome Measures)**

Domain	Subdomain (measure name)	Test
Cognition	Premorbid Estimate	Wide Range Achievement Test-4 (WRAT-4)
	Attention & Information Processing Speed	Trail Making Test
	Executive Functioning	Clock Drawing Test Controlled Oral Word Association Test (letter & category)

		Wisconsin Card Sorting Test (WCST)
	Language Functioning	Boston Naming Test (BNT), Language Screen
	Motor Skill	Grooved Pegboard
	Visuospatial Skill	Judgment of Line Orientation (JLO)
	Memory	Benton Visual Memory Test-Revised (BVMT-R)
Emotion (Self- Report)	Mood	Geriatric Anxiety Inventory (GAI) Geriatric Depression Scale (GDS)
Validity	Effort	Rey 15 Item Test

### Magnetic Resonance Imaging (MRI)

MRI Safety Screening: Site-specific MR safety screening procedures will be followed. All participants will be screened for medical devices, implants, and metal prior to undergoing MRI, first on the telephone, and again prior to entering the scanner room. If it is necessary to review medical records to confirm contraindication, a review of medical records (e.g. previous surgeries) will take place prior to the scheduled visit. Prior to entering the MRI scan room, an x-ray exam may be completed as a safety precaution on subjects who might have metal in body (for example, an orbital x-ray, or x-ray of another body part). During the telephone screening process, participants will also be questioned about their ability to temporarily remove transdermal patches (such as birth control or nicotine patches). Women of child-bearing potential will be asked to confirm that they are not pregnant when signing the Informed Consent Form. If a woman has concerns or is uncertain of her pregnancy status, she will be excluded, as the risks of an MRI scan to pregnant women are currently unknown. The risks are minimal for a properly administered visit. The MR technicians are trained and prepared to deal with any problems that may arise.

We will collect a full suite of non-invasive anatomical and blood flow scans using GE 3.0 high-field scanners running the newest operating system and a 32-channel head coil. All participants are prepped and trained prior to the procedure. The MRI protocol will consist of anatomical and other advanced scans including ASL perfusion and DTI. These scans will be conducted over one session which will take approximately 60 minutes including set-up and instructions but could take longer depending on participant set-up time or need to repeat instructions. The sequences, protocols, parameters, and/or scan order may be modified during the study based on new scientific information or technical factors.

The MRI scanner is an Investigational Device of Non-Significant Risk: The MRI scanner to be used in the study is considered an investigational device due to the investigational software used in the study that was developed by the collaborators at both MCW and UW-Madison. However, the Magnetic Resonance Imaging (MRI) device is an FDA cleared device for safe and non-invasive imaging of the interior of the human body. The MRI scanner is also considered an investigational device when the 32-channel head coil is used. Modified pulse sequences include T1-weighted MPnRAGE, pseudocontinuous arterial spin labeling (pcASL), and simultaneous multislice (SMS) echo planar imaging for diffusion-weighted imaging (DWI). These pulse sequences were developed by medical physics experts using the EPIC pulse sequence development environment provided by GE Healthcare, which constrains the pulse sequences to operate within the FDA limits for safe operation with respect to gradient switching (dB/dt) and RF power (SAR). The proposed modified MRI pulse sequences (developed at MCW and UW-Madison), and the 32-channel head coil are not implantable devices, are not intended to support or sustain human life; are NOT for a use of substantial importance in diagnosing, curing, mitigating, or treating disease or otherwise preventing impairment of human health and they do not present a potential for serious risk to the health, safety, or welfare of a subject. The scanner also restricts research software from exceeding FDA safety levels. The scanner monitors the specific absorption rate (SAR) for research scans just as it does for

all other scans. Thus, the scanner with the investigational software fully engaged operates, from a technical design and functional standpoint, as a non-significant risk device in accordance with 21 CFR 812. By staying below these limits, the operating conditions of the MRI device are generally deemed, in and of themselves, to make the MRI device a non-significant risk device.

The Nova Medical 32-channel head coil (model number NMSC075-32-3GE-MR750) is an investigational device not FDA approved for clinical use. This coil device includes multiple features for safe operation involving human studies. The 32-channel coil is designed and constructed as a receive-only detector of RF signals that are emitted by the brain following the RF excitation generated by the GE MRI scanner, which is FDA approved. During the RF excitation by the scanner, the coil device is decoupled (made inactive) through redundant circuitry, thus the coil device never transmits RF to the subject, so it has no impact on subject risk or safety.

More specifically, the coil design and construction include the following safety features: (1) High voltage breakdown (>2kV) UL-94V0 flame retardant housing. (2) Rugged construction to assure safe operation in case of rough handling. (3) Active detuning circuitry providing greater than 35 db isolation per element. (4) High power passive detuning circuits in case primary detuning circuitry fails. (5) Multiple common mode traps in all receive coil cables. (6) Minimum of 5mm spacing between coil conductors and patient contact.

Additionally, the coil was designed and manufactured under an ISO 13485 certified quality management system. As part of this quality system, Nova Medical has conducted a Failure Means and Effects Analysis (FEMA) of this product and we feel that it is a non-significant risk under foreseeable normal conditions when used on the 3T GE X750 MRI scanners at MCW and UW-Madison.

**Mock Scanner Training.** Participants will be offered the option to engage in a mock scanner training session. The purpose of this session is to acclimate participants to the scanner and to assess their comfort level, minimize any anxiety, and provide practice and training to remain still. Training in the mock scanner will take approximately 20 minutes and will occur prior to their imaging sessions. A visual feedback system will be employed to inform the subject about her or his performance of remaining stationary. Further, contoured padding will be employed to physically ensure subject stability throughout the imaging session. After the session, any questions or concerns will be discussed. Participants that have been previously engaged in MRI as part of research may be excused from the mock scanner training.

## 10.2 Treatment and Follow-up Visits

After subjects have been enrolled, the On-Study/Follow-up visits and the procedures performed at each visit are described in detail below.

### Treatment

#### Visits 2-16\*

At these visits, the following will occur:

- Cognitive training with HD-tDCS treatment OR
- Cognitive training with sham HD-tDCS treatment
- On Mondays prior to CT and Fridays after CT, subjects will be assessed on competency and ability to perform the CT.

These visits will likely last about 2.5 to 3 hours.

**\*Missed or rescheduled treatment visits:** Because there may be a benefit from a single treatment session at any point during the study, subjects who miss or need to reschedule treatment visits will be eligible to complete their missed visit at any point prior to Month 3 procedures.

### **Visit 17 (Month 3)**

At this visit, the following procedures and tests will occur:

- Neuro and physical exam
- Vitals signs
- Cognitive battery
- Study Partner Questionnaires
- Structural MRI (will aim to be completed within 6 week window, but can be completed up to 12 months after Visit 16 if scheduling problems arise)

This visit will be approximately 6 hours and will likely be completed in 1-2 days but can be completed over multiple days.

### **Visit 18 (Month 6)**

At this visit, the following procedures and tests will occur:

- Cognitive battery
- Study Partner Questionnaires

This visit will be approximately 4 hours and will likely be completed in 1 day but can be completed over multiple days.

## **10.3 Unscheduled Visits**

The reason for an unscheduled visit will be an unexpected or serious adverse event.

## **10.4 Early Termination/Withdrawal Visit**

Subjects who are either withdrawn or terminated early from the study will have one final visit to report adverse events.

## **11.0 DATA COLLECTION, HANDLING, SHARING, AND RECORD KEEPING**

### **11.1 Data Collection**

#### **Data Collection Forms**

Standardized data collection forms (e.g., source documents, case report forms, standardized assessment forms, etc.) are used to ensure data collected are consistent and compliant with the protocol and IRB application.

Data collection is the responsibility of study team members under the supervision of the Principal Investigator (PI). The PI is responsible for ensuring the accuracy, completeness, legibility, and timeliness of the recorded and reported data.

Data collection forms are maintained in the subject files and retained as described in Section 11.3: Records Retention.

## 11.2 Confidentiality and Privacy

Participants' privacy will be protected with the utmost care. We recognize the diagnosis of MCI or Alzheimer's disease, may cause embarrassment and/or discrimination. We will handle all contacts with participants with special attention to privacy. General mailings (not related to specific appointments) will be sent in discrete envelopes. Personnel making phone contacts will be trained to protect privacy when leaving messages or talking with family members who answer the phone. All research procedures will be conducted in private settings, and only information absolutely necessary to conduct our research will be gathered.

Information about study subjects will be kept confidential and managed according to HIPAA requirements. All subjects will sign a combined informed consent and HIPAA authorization form that includes specific privacy and confidentiality rights. Study data will be maintained per federal, state, and institutional data policies.

The investigator(s) will ensure that the identities of subjects are protected by using coded subject information. The log of subject identifying information that links subjects to their study-specific identification number will be maintained by the investigator. The log and all study records will be maintained in locked spaces and access will be limited to the PIs and coordinators. Electronic study records/files will be stored on a dedicated server and accessed via networked computers that are password-protected with access provided only to authorized study personnel.

## 11.3 Records Retention

It is the investigator's responsibility to retain study essential documents for a minimum period of 7 years following completion of the study per MCW and UW-Madison institutional policy.

## 11.4 Protocol Deviations

A protocol deviation is any noncompliance with the clinical trial protocol or investigational plan requirements. The noncompliance may be either on the part of the subject, the investigator, or the study site staff. As a result of deviations, corrective actions are to be developed by the site and implemented promptly.

It is the responsibility of the Principal Investigator/site investigator/study staff to use continuous vigilance to identify and report deviations. The Principal Investigator is responsible for assessing whether the deviation constitutes noncompliance as defined by the reviewing IRB and if so, reporting it within the required time frame(s). The site investigator is responsible for knowing and adhering to the reviewing IRB requirements.

# 12.0 STUDY ANALYSIS

## 12.1 Statistical Hypotheses

- **Primary Efficacy Endpoint(s):**

Treatment completion rates.

- **Secondary Efficacy Endpoint(s):**

- Consent rate.
- ADCS-PACC score at 3 and 6 months
- Neurite density (intracellular volume fraction) at 3 months
- Diffusivity indices: Fractional anisotropy (FA), Mean(MD), Axial(AD), Radial(RD) Diffusivity at 3 months
- Morphometric indices: Cortical thickness, Surface Area, Volume, gyration index at 3 months
- ASL perfusion indices: blood flow, blood volume, mean transit time, time to peak, at 3 months

## 12.2 Sample Size Justification

Given the pilot nature of this study, two feasibility outcomes will be included: Consent rate and treatment completion rate. 20 patients are enough to calculate a 90% exact binomial confidence interval of (.75, 1) if all 20 are observed to complete treatment. Thus, this sample size is large enough to potentially exclude completion rates of 3/4 or lower. The pilot data from this study will provide initial estimates of the variability and the effect sizes; This information will then be used for the formal calculations of power and sample size necessary to conduct a future phase II trial.

This pilot study, if successful, would prove the feasibility of the proposed approach. Treatment completion rates of less than 75% could be reasonably excluded if all 20 patients are observed to complete treatment. Additionally, recruiting and consenting 20 patients over a period of 3 months would support the feasibility of conducting a larger-scale, 2-site, phase II trial with 120 MCI patients over a span of 5 years (i.e. approximately 32 patients/year). This would be the necessary next step in the path to using combined HD-tDCS/CCT as an intervention that could lead to tangible clinical improvements. This future trial would use a 2 X 2 factorial design that would allow for the inclusion of a 'true' control group (i.e. sham HD-tDCS/sham CCT). The stimulation period would be extended (six months instead of three) with the hope of inducing longer lasting effects that could translate into a slowing of disease progression; Accordingly, we would evaluate the effects of the intervention at 6, 12 and 18 months. MRI changes would be assessed at 12 months, as well as the effect on cerebrospinal fluid (CSF) AD biomarkers of a subset of patients. **Sample size justification for future phase II trial (N=120)**. Driven by the efficacy outcome of change in ADCS-PACC score from baseline to 12 months. We presume that 10% of these patients are lost to follow up before one year. We further presume that the main aim will be addressed by a two-sided test at the .05 level of the hypothesis that the improvement rate in the true HD-tDCS group exceeds that of the sham group. Under these assumptions there is a minimum 90% power to detect a 31% difference in improvement rates. Thus, this design has good power to find a moderate effect size of HD-tDCS treatment.

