	
 
• Consent rate
 
• ADCS PACC score at 3 and 6 months
 
• Neurite density (intracellular volume fraction) at 3 months
 
• Diffusivity indices: Fractional anisotropy (FA), Mean (MD), Axial (AD), Radial (RD)
 
• Diffusivity at 3 months
 
• Morphometric indices: Cortical thickness, Surface Area, Volume, gyration index at 3 months.
 
• ASL perfusion indices: blood flow, blood volume, mean transit time, time to peak, at 3 months
 

Study Design	The study design is a double-blinded, randomized pilot clinical trial of HD-tDCS/sham HD-tDCS combined with CT, administered to subjects with amnestic MCI (aMCI) in blocks of 5 daily treatments for a total of 15 sessions. There will be one treatment block/month for a total of 3 months. 20 participants with aMCI will be enrolled. There will be 2 treatment groups/arms with 10 subjects per group/arm. We anticipate a dropout rate of appr. 10% and aim to complete procedures in 20 subjects.
Study Intervention	High definition transcranial direct current stimulation (HD-tDCS) Sham HD-tDCS Computerized Cognitive training (CCT) Sham CT
Total Number of Subjects	20
Study Population	Male and females aged 50 to 90 years with established diagnosis of MCI amnestic type. Total of 20 subjects
Statistical Methodology	Given the pilot nature of this study, two feasibility outcomes will be included: Consent rate and treatment completion rate. 20 patients are enough to calculate a 90% exact binomial confidence interval of (.75, 1) if all 20 are observed to complete treatment. Thus, this sample size is large enough to potentially exclude completion rates of 3/4 or lower. The pilot data from this study will provide initial estimates of the variability and the effect sizes. This information will then be used for the formal calculations of power and sample size necessary to conduct a future phase II trial.
Estimated Subject Duration	The duration of the study for each subject is approximately 6 months.
Estimated Enrollment Period & Study Duration	Study enrollment and follow-up will occur over 9 months with the total expected duration of the trial to be 12 months.

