## **9.4 Study Intervention Compliance**

Threshold adherence/compliance is achieved when the enrolled participant completes all HD-tDCS/sham HD-tDCS + CT sessions and undergoes cognitive testing at 0, 3 and 6 mo. This degree of participation will allow calculation of the primary outcome, i.e. treatment completion rates.

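### The 90% exact interval for 20 of 20 completers is (.86, 1), not (.75, 1) as the synopsis and section 12.2 state

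*Combined protocol and SAP*

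**What the plan says.** The primary endpoint is the treatment completion rate. Section 9.4 ties it to completing all stimulation-plus-training sessions and the cognitive testing at 0, 3 and 6 months, and adds: "This degree of participation will allow calculation of the primary outcome, i.e. treatment completion rates".

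The only numerical support for N = 20 on this endpoint is in section 12.2: "20 patients are enough to calculate a 90% exact binomial confidence interval of (.75, 1) if all 20 are observed to complete treatment". The Statistical Methodology row of the synopsis (3.1) gives the same interval. Section 12.2 then interprets it: "Thus, this sample size is large enough to potentially exclude completion rates of 3/4 or lower", and further on: "Treatment completion rates of less than 75% could be reasonably excluded if all 20 patients are observed to complete treatment". The synopsis also says: "We anticipate a dropout rate of appr. 10% and aim to complete procedures in 20 subjects".

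**The concern.** The plan states the method (exact binomial), the confidence level (90%), the sample size and the observed count, so the interval can be checked directly. It does not reproduce.

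Two things follow. First, the one precision figure offered for the primary endpoint is wrong in both places where it appears, and it understates what 20 patients can show. Second, if the lower limit at 20 of 20 really were .75, any smaller count would have a limit below .75, so a single non-completer would make it impossible to exclude 75%. A reader who trusts the printed figure would misjudge a result of 19 of 20. The plan anticipates some dropout, and the definition of completion in 9.4 is strict, so results short of 20 of 20 are the ones most likely to need interpreting.

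**Working it through.** **Inputs.** n = 20 and x = 20 completers, 90% exact binomial interval, and a completion rate to be excluded of .75 or lower, all from section 12.2 (n, x and the interval also in 3.1). Sidedness is not stated. An interval quoted with two limits is normally two-sided, with 5% in each tail; the one-sided reading was also tried.

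**Attempt to reproduce the plan's figure.** When x = n, the Clopper-Pearson lower limit is (tail area)^(1/n) and the upper limit is 1.

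| Method at 20 of 20 | Lower limit |
|---|---|
| Exact, two-sided 90%: 0.05^(1/20) | .861 |
| Exact, one-sided 90%: 0.10^(1/20) | .891 |
| Exact, two-sided 95%: 0.025^(1/20) | .832 |
| Exact, two-sided 99%: 0.005^(1/20) | .767 |
| Mid-p, 90% | .891 |
| Wilson, 90% | .881 |
| Agresti-Coull, 90% | .859 |
| Jeffreys, 90% | .910 |
| Plan | .75 |

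None gives .75. Working backwards, .75^20 = .0032, so a lower limit of .75 at 20 of 20 corresponds to two-sided confidence of 1 − 2 × .0032 = .994, not .90.

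**How many completers exclude 75%?** For x < n the two-sided 90% lower limit is the 5% quantile of a Beta(x, n − x + 1) distribution. Equivalently, 75% is excluded when P(X ≥ x | p = .75) is below .05 (two-sided 90%) or below .10 (one-sided 90%).

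| Completers | Two-sided 90% exact | One-sided 90% lower bound | P(X ≥ x) at p = .75 |
|---|---|---|---|
| 20 of 20 | (.861, 1) | .891 | .0032 |
| 19 of 20 | (.784, .997) | .819 | .0243 |
| 18 of 20 | (.717, .982) | .755 | .0913 |

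For 19 of 20 the tail is 20 × .75^19 × .25 + .75^20 = .0211 + .0032 = .0243. So 19 completers exclude 75% on the two-sided 90% interval, and even on the two-sided 95% interval, whose lower limit is .751. With 18 completers the answer depends on sidedness: 75% is not excluded two-sided (.717), but is excluded one-sided (.755).

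**What the difference is worth.** The documents give no assumed completion rate, so this is a range under assumed rates, with n fixed at 20 and patients independent.

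| Assumed true completion | P(all 20 complete) | P(at least 19 complete) |
|---|---|---|
| 85% | .04 | .18 |
| 90% | .12 | .39 |
| 95% | .36 | .74 |

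**The case against.** The arithmetic is not in dispute, but there is a fair case that little turns on it.

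- **The error is conservative.** The plan's statements about 20 of 20 are true as worded. Section 12.2 gives a sufficient condition, "if all 20 are observed to complete treatment", and nowhere says that fewer completers would fail. This stands. The 19-of-20 point is an inference from the printed limit, a consequence of the wrong number and not a second error. The inference is nonetheless sound, because the lower limit falls as the count falls.
- **Nothing operational uses the interval.** No success threshold depends on it, section 12.4 does not refer to it, there is no interim analysis (12.5), and the interval reported at the end would be computed from the data. This stands too, and it limits the weight of the point.
- **Sidedness is a side issue.** A two-limit interval is conventionally two-sided, and neither reading yields .75. That is right as far as the error goes. Sidedness matters only for reading 18 of 20.
- **The denominator may not be 20.** Section 7.2 ends the study when 20 subjects have completed, and section 8.6 replaces subjects who are randomized but never treated, while not replacing treated subjects who withdraw. If enrolment continued until 20 completed, the denominator could exceed 20, and the 19-of-20 and 18-of-20 results would not apply as they stand. The corrected .861 is unaffected, because the plan's own statement is conditional on 20 of 20.

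**Conclusion.** The printed interval is wrong. At 20 of 20 the two-sided 90% exact lower limit is .861, not .75, a difference of about 11 percentage points, and no usual convention closes the gap. The plan's conclusion survives: 20 of 20 excludes completion rates of 75% or lower, and the choice of 20 patients is not weakened. What does not survive is the implication that a perfect result is needed. With a denominator of 20 and a two-sided 90% exact interval, the smallest count that excludes 75% is 19.

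This should be corrected because it is the only figure supporting the sample size for the primary endpoint. It does not threaten the trial. The correction at 20 of 20 rests only on the method, level and counts the plan itself states. The statements about 19 and 18 completers also assume a denominator of exactly 20.

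**What to change.** 1. In 3.1 and 12.2, replace (.75, 1) with (.86, 1) and name the interval as a two-sided 90% exact (Clopper-Pearson) interval. This alone cures the error.
2. Preferably add one sentence in 12.2, stated for a denominator of 20: completion rates of 75% or lower are also excluded with 19 of 20 completers (.784 to .997), but not with 18 of 20 (.717 to .982). This describes precision and does not set a pass mark; the plan has none, and whether to have one is the sponsor's choice.
3. If a one-sided 90% bound is intended, say so now: the limit at 20 of 20 is then .891, and 18 of 20 (.755) does exclude 75%. Settling this before results are known avoids choosing afterwards.
4. If a probability of reaching 19 of 20 is quoted, give it as a range with its assumptions (about .18, .39 and .74 at true completion of 85%, 90% and 95%). Do not derive the completion rate from the anticipated 10% dropout, because completion as defined in 9.4 need not equal one minus dropout.

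The cost is a corrected number and some wording in two places. There are no extra patients and no change to N or to the analysis.
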